For the families enrolled in Aim 2 of the RCT or the ancillary project, study activities include the completion of 4 surveys: T1, T2, T3, and T4. Should a family member be enrolled into the RCT under an ICU clinician who has been randomized to intervention, a family meeting will occur between the randomized clinician and the family member to discuss the reported needs from T1. This family meeting will occur after T1 is completed but prior to T2 survey completion. Clinicians enrolled into the RCT and randomized to the intervention arm will be able to view the family needs data.

This study represents minimal risk. We have specific plans to address potential distress occurring during the study, as well as plans to protect against the potential loss of data confidentiality.

Research Summary

State your primary study objectives

The primary objective of the RCT is to compare the web app (ICUconnect) to usual care on unmet needs and perceptions of quality of care. The secondary objective is to determine the effect of the web app (ICUconnect) as an intervention on racial disparities in both unmet needs and in the quality of patient-centered care within the Duke University Hospital Intensive Care Units (ICUs) and Durham Regional ICUs. The ancillary study aims to understand how ICU patients' and their families' palliative care needs in an ICU setting evolve over time and develop a needs-targeted, ICU-based palliative care collaborative delivery model.

Using a multi-aim approach, we hypothesize that by conducting the RCT and ancillary studies simultaneously that we will be able to:

- 1. Optimize the usability of the ICUconnect web app intervention (Aim 1, RCT)
- 2. Find that the intervention (web app, ICUconnect) will improve:
 - a. Unmet needs in both Black and White patients and families in the ICUs (Aim 2, RCT).

- b. Quality of patient-centered care in both Black and White patients and families in the ICUs (Aim 2, RCT).
- 3. Find that the intervention (web app, ICUconnect) will improve:
 - a. Reduce racial disparities in unmet needs and quality of patient-centered care for patients and families in the ICUs (Aim 3, RCT)
- 4. Understand the type, severity and burden of the needs of patients and families and thereby develop a method to decrease psychological distress and develop a collaborative care delivery model for ICU clinicians (Aim 1 and 2, Ancillary)

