
Aims 2 and 3 of the RCT will be completed simultaneously. The total targeted population for Aims 2 and 3 of the RCT are 240 enrolled patient/family dyads and a maximum of 60 randomized clinicians. To be considered "enrolled" for this study, a patient/family dyad must meet all eligibility criteria and receive a NEST score of > 15.

For aims 2 and 3, the study team will conduct a randomized clustered clinical trial. Randomization occurs at the ICU clinician level versus that of the patient/family level. Clinicians are identified as eligible if they are the current attending on service for the particular ICU. Clinicians are randomized to one of the two arms based on the following:

- 1. Gender (male/female)
- 2. Clinical Experience (<10 years vs > 10 years)
- 3. Discipline (medical vs. surgical)

Consented, enrolled clinicians are expected to complete the following survey(s):

• Baseline Demographics Survey (on the day of consent)

For those clinicians who are randomized to intervention, they will be required to complete the following:

- Review patient/family needs score and survey results within ICUconnect (at the completion of T1 by patient/family dyad)
- Schedule and conduct a family meeting (after T1 completion but before T2 completion)
- Review patient/family needs score and survey results within ICUconnect (at the completion of T2 by patient/family dyad)
- Complete the Clinician Survey via ICUconnect (after Family Meeting and completion of T1 and T2 by patient/family dyad).

Patient/family dyads will be identified at the time of ICU admission and approached for consent based on meeting study inclusion/exclusion criteria (see Selection of Subjects). Each patient/family member, if enrolled into the RCT will be asked to complete an ICUconnect profile and survey (T1). This survey is to be completed within 24 hours of consent to the study. Given that this study's intent is to address unmet needs, eligible participants must receive a NEST score of > 15 (see Study Eligibility Workflow).

- If a participant receives a NEST score of < 15 and they are assigned to a randomized intervention clinician, the participant is considered a screen failure.
- If a participant receives a NEST score of < 15 and is assigned to a randomized control clinician, the
 participant is considered a screen failure for the RCT but is allowed to continue participation within
 the ancillary study.

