Assuming that a participant receives a NEST score of \geq 15, regardless of clinician randomization, the participant will continue with the following study procedures:

- Survey 2 (T2) to be completed within 3 days (0/+1 day) of T1 completion.
- Survey 3 (T3) to be completed within 7 days (0/+3 days) of T1 completion
- Survey 4 (T4) to be completed within 3 months (90 days, 0/+3 days) of T1 completion.

Should a participant receive a NEST score of \geq 15 and be randomized to an intervention clinician, the participant will be contacted by the intervention clinician have a family meeting. Family meetings are to occur after the completion of T1 but prior to the completion of T2. Given the short timeframe between T1 and T2, the clinician can conduct the family meeting in a variety of settings: in the ICU at bedside, in a private conference room and/or location within the waiting room (at the choice of the participant), and/or over the phone.

In conjunction with Aims 2 and 3 of the RCT, the study team will simultaneously enroll patient/family dyads into the ancillary study. The ancillary study will include a total of 250 enrolled patient/family dyads. Eligible participants will be approached for consent at the time of the ICU admission. Participants enrolled into the ancillary study will be those participants whose current attending clinician is not enrolled in the RCT and/or their identified primary race and ethnicity is something other than White or African American /Black and Non-Hispanic. Participants enrolled in the ancillary study, like the RCT, must meet study eligibility criteria.

Participants enrolled into the ancillary study will complete an ICUconnect profile and then be asked to complete the following surveys:

- Survey 1 (T1) to be completed within 24 hours of consent.
- Survey 2 (T2) to be completed within 3 days (0/+1 day) of T1 completion.
- Survey 3 (T3) to be completed within 7 days (0/+3 days) of T1 completion
- Survey 4 (T4) to be completed within 3 months (90 days, 0/+3 days) of T1 completion.

Given that the targeted patient population involves individuals who are seriously ill and/or injured, the study team expects that there is a high likelihood that death could occur while the patient/family dyad's participation is ongoing. Should a patient pass away while study participation is ongoing, the following will occur:

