Inclusion Criteria (Family Member)

1. Must have been previously consented and enrolled in the ancillary and/or RCT study, meaning that all eligibility criteria noted above was met both pre and post consent.

Exclusion (Family Member)

Subject Recruitment and Compensation

Describe recruitment procedures, including who will introduce the study to potential subjects. Describe
how you will ensure that subject selection is equitable and all relevant demographic groups have access
to study participation (per 45 CFR 46.111(a) (3)). Include information about approximately how many
DUHS subjects will be recruited. If subjects are to be compensated, provide specific prorated amounts
to be provided for expenses such as travel and/or lost wages, and/or for inducement to participate.

All eligible patient/family dyads, regardless of RCT or ancillary study, are recruited from within the participating ICU. Recruitment of eligible patient/family dyads can occur in 1 of 3 ways, depending on the patient/family dyad at the time of consent:

- 1. Traditional research introduction and in-person consent: the study team will approach a member of the clinical team who is facilitating in the care and communication with the eligible patient/family dyad. The study team will inform the clinical team member (typically the registered nurse in charge of the patient's room) that the patient/family dyad are eligible for participation in a research study. A brief explanation of the research study will be provided to the clinical team member. Given the sensitive nature of the targeted study population (at risk for death and/or disability), the study team will ascertain from the clinical care team member if it is an appropriate time to speak with the patient/family dyad. If the clinical care team member says that it is okay, the clinical care team member will be asked to provide a research introduction to the patient/family dyad. Assuming that a verbal "okay" to approach is provided, the study team will approach and provide a brief review of the study (verbally and/or utilizing the brief study infomercial) and ask if they would like to review the informed consent. Should the patient/family dyad be interested, the study team member will proceed with either eConsent or traditional paper consent, at the request and preference of the patient/family dyad.

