Please note that for all scenarios described above, a research introduction may also be completed by the investigators of this study, as they all are routinely physicians on service and dually serve as members of the clinical care team. Research introductions for eligible patient/family dyads provided by investigators will be used as infrequently as possible and only when necessary. This will ensure that coercion to participate in the study is minimized as much as possible.

Eligible clinicians will be introduced to the research study by the investigators of the study. All eligible clinicians will be approached and provided a brief research introduction. If the clinician is interested in participation, he/she will provide verbal or written affirmation to the investigators. The investigators will then inform the study team of the clinician's interest in the study and confirm that it is okay to approach for research. The study team will then contact the clinician, due to their busy schedule, electronically and provide the eConsent (unless otherwise requested by the clinician, in which case paper consent would be utilized).

For the RCT, specifically, the study includes only those participants who self-identify as non-hispanic and either white or black. The purpose of this design is to determine racial disparities experienced among black patients and their families. However, the ancillary study is open to all races and ethnicities and will therefore ensure that the subject selection for this entire project is equitable and all relevant demographic groups have access to study participation.

To meet the statistical power needs for data analysis, the RCT intends to consent approximately 320 patient/family dyads to ensure that 240 patient/family dyads meet all study criteria and are subsequently enrolled. In order to enroll 240 patient/family dyads, 30-60 clinicians will be consented, enrolled and randomized to the study with a relatively equitable split between those clinicians assigned to intervention and those assigned to control.

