Approach to statistical models: The goal of the primary hypothesis (2a) is to determine the efficacy of the ICUconnect intervention versus usual care on reduction in unmet needs from T1 to T2. Additionally, we are interested the intervention effect within Black families and White families separately. Unmet needs will be assessed at T1 and T2 with the total NEST score, a continuous, normally distributed measure. Because each family member is surveyed at multiple time points and the same ICU physician sees several patients, outcome variable measurements will not be independent. We, therefore, plan to use hierarchical linear models as our primary analytic strategy because they appropriately account for the multiple types of correlation inherent in our study design.45 The hierarchical linear model will have the following form: Yijk= b0+ b1(T2) + b2(T2*intk) + b3(racek)+ b4(servicetimek) + b5(ICUtypek)+ bik+ ck+ eijk, where Yijkis the total NEST score for family iat time jand physiciank. In this model, T2and intare indicator variables for the post-treatment and intervention group, respectively. Additionally, we include indicators for the randomization stratification variables. The multiple levels of correlation are captured via the physician-level random effect, ck, and the family-level random effect, bjk. Both random effects and the residual error (eijk) are assumed to be independent and normally distributed. PROC MIXED in SAS (SAS Inc., Cary, NC) will be used to fit the hierarchical linear models and test the primary hypothesis (2a). Specifically, if b2is negative and significantly different than zero, this provides evidence families in the intervention group have reduced unmet needs as compared to usual care group families. The secondary outcome, quality of patient-centered care, is also a continuous measure assessed at T1 and T2. A similar hierarchical linear model will be used to test Hypothesis 2b; in this model, if b2is positive and significantly different than zero, this provides evidence families in the intervention group have improved quality of patient-centered care as compared to usual care group families. Both analyses for Hypotheses 2a and 2b will be repeated within Black and White patients separately, with the goal to ensure that the intervention is effective in both subgroups (as an overall treatment effect can sometimes mask important heterogeneity). Aim 3 addresses relative differences in the intervention effect on reducing disparities.

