
Power and sample size considerations. For Aim 1, to reach a target of 'excellent' usability (mean SUS score >85), we expect 1-2 iterative revision cycles of 8-15 family members and 8-10 clinicians—a sample similar in size to that needed to reach thematic saturation in qualitative analysis (e.g., the 30 patient-level cases (total n=90) we expect will allow us to recognize theme saturation in Aim 4). The effect of interest for Aims 2 and 3 is essentially the T1 - T2 difference between the intervention and usual care groups. Aim 2 focuses on the overall difference and the difference within Black and White patients separately, while Aim 3 focuses on the difference within Black families compared to White families. Therefore, we base our sample size calculations on the mean difference score using tests for two means in a cluster randomized design. The sample size requirements are greatest for Aim 3; as discussed by Leon and Heo (2009), the needed sample size for the family race by intervention group interaction is 4 times that needed for the overall test. Based on preliminary studies, the standard deviation of the change in NEST score is estimated as 12 units and a reasonable range of intraclass correlation coefficients is 0.01 to 0.1. For all calculations, the type I error is 5% and power is 80%. With a sample size of 160 families (4 per each of 40 physicians. 20 per treatment arm), we will be able to detect differences of 4.0 to 5.0 NEST units for Hypothesis 2a in the overall test, 5.4 to 6.1 for Black or White patients separately, and 7.6 to 8.0 units for Hypothesis 3a. For Aim 4, we expect that up to 25 cases comprised of family members will be sufficient to reach informational redundancy—the point at which no new themes emerge.

Ancillary study: Needs and triggers: improving intensive care unit-based palliative care deliveryStatistical methods:

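### Families are recruited after their clinician is randomised, no safeguard is described that hides the arm from those who introduce, consent or administer T1, and the primary model assumes equal T1 means

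*Protocol*

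**What the plan says.** Protocol, Design & Procedures: "Randomization occurs at the ICU clinician level versus that of the patient/family level". The Research Abstract confirms the order, since the family meeting applies "Should a family member be enrolled into the RCT under an ICU clinician who has been randomized to intervention". Study Interventions likewise assigns each RCT family to a clinician who has already been randomised. The clinician's trial status is consulted at recruitment: "Participants enrolled into the ancillary study will be those participants whose current attending clinician is not enrolled in the RCT" (a family's race or ethnicity may also direct it there). The power section plans several families per clinician: "With a sample size of 160 families (4 per each of 40 physicians. 20 per treatment arm".

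Subject Recruitment and Compensation gives three routes to a family. On the first, "the study team will ascertain from the clinical care team member if it is an appropriate time to speak with the patient/family dyad", and that team member, typically the nurse, then makes the introduction. On the second, the clinical team introduces the study and consent is remote. On the third, the study team uses an approved script with no clinical introduction. For all three, "a research introduction may also be completed by the investigators of this study, as they all are routinely physicians on service". The limit is that "Research introductions for eligible patient/family dyads provided by investigators will be used as infrequently as possible and only when necessary", and the reason given is to minimise coercion.

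The Aim 2 equation begins "b0+ b1(T2) + b2(T2*intk" and continues with the stratification terms and random effects for physician and family. It has no main effect of intervention. The Aim 3 equation has neither an intervention main effect nor a Black-by-intervention term at baseline. The SAP names hierarchical linear models, writes no equation and lists no sensitivity analysis for baseline imbalance.

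**The concern.** In a cluster trial that recruits participants after allocation, randomisation balances the clinicians but not necessarily the families who enter under them. If people who influence entry know the arm, the families can differ between arms from the start.

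The duties here differ by arm. An intervention clinician must review scores, hold a family meeting before T2 and complete a survey, without payment; a control clinician does none of this. A team could, without bad faith, judge a difficult family not ready to be approached more often in one arm than in the other.

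A common T1 mean is a sound constraint when participants are identified before allocation. When they are not, the constraint turns part of any real baseline difference into apparent treatment effect. The error can run either way. A lasting difference biases b2 in its own direction, so intervention families who enter with lower need make the intervention look better, and families with higher need make it look worse.

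**Working it through.** **The plan's own figure.** For 160 families (80 per arm, m = 4, SD of change 12, two-sided 5%, 80% power) the protocol states a detectable difference of 4.0 to 5.0 units for Hypothesis 2a. The usual formula is (1.96 + 0.842) × 12 × √{(2/80)[1 + 3·ICC]}. It gives 5.39 at ICC 0.01 and 6.06 at ICC 0.1, so the stated figure is not reproduced. That is a separate matter. The figures serve below only as a yardstick, and both versions are used.

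**Inputs from the protocol.** 40 physicians, 20 per arm, 4 families each; SD of change 12; ICC 0.01 to 0.1. In the Aim 2 model both random intercepts cancel from a change score, so the residual variance is σe² = 12²/2 = 72.

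**Assumptions not in the documents.** T1-T2 correlation ρ of 0.3, 0.5 or 0.7; the stated ICC range read as the physician share of total NEST variance; equal cluster sizes; stratification covariates left out; a baseline difference d (intervention minus control) of 3 units for illustration.

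**Formula.** Total variance V = 72/(1−ρ), physician variance σc² = ICC·V, family variance σb² = ρV − σc². The correlation of a physician's mean T1 with mean T2 is

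R = (σc² + σb²/m) / (σc² + σb²/m + σe²/m).

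With a common T1 mean, b2 is the T2 difference minus R times the T1 difference. A difference that persists to T2 therefore gives bias (1−R)d. One present at T1 only gives −R·d.

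**One end, ρ = 0.3, ICC 0.01.** V = 102.9, σc² = 1.03, σb² = 29.83. R = (1.03 + 7.46)/(8.49 + 18) = 0.32, so the lasting bias is 0.68d.

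**Other end, ρ = 0.7, ICC 0.1.** V = 240, σc² = 24, σb² = 144. R = (24 + 36)/(60 + 18) = 0.77, so the lasting bias is 0.23d.

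| ρ | ICC | lasting bias | T1-only bias | bias, lasting d = 3 | SE of b2 | type I error, lasting d = 3 |
|---|---|---|---|---|---|---|
| 0.3 | 0.01 | 0.68d | −0.32d | 2.04 | 1.54 | 26.2% |
| 0.3 | 0.1 | 0.54d | −0.46d | 1.62 | 1.62 | 16.9% |
| 0.5 | 0.01 | 0.49d | −0.51d | 1.46 | 1.65 | 14.3% |
| 0.5 | 0.1 | 0.38d | −0.62d | 1.15 | 1.71 | 10.4% |
| 0.7 | 0.01 | 0.29d | −0.71d | 0.87 | 1.75 | 7.9% |
| 0.7 | 0.1 | 0.23d | −0.77d | 0.69 | 1.78 | 6.7% |

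The SE is √{(2/20)(σc² + σb²/4 + 18)(1 − R²)}. Type I error is the chance that |Z| exceeds 1.96 when Z has mean bias/SE and variance 1.

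**Yardstick.** Pairing like ICC with like, the bias for d = 3 is 14% (0.69/5.0) to 51% (2.04/4.0) of the stated detectable difference, or 11% (0.69/6.06) to 38% (2.04/5.39) of the recomputed one.

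**Other sample size.** Design & Procedures targets 240 dyads. With 40 physicians of 6 families the lasting share is 0.20 to 0.67, essentially the same.

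**With an intervention main effect.** b2 becomes the difference in change scores. The bias is 0 for a lasting difference and −1.0d for a T1-only difference. The SE is √{(2/20) × 2 × 18} = 1.90 in every row.

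**The case against.** The strongest reply is that the documents never say that anyone who recruits knows the arm. Sending a family to the ancillary study because its attending is outside the RCT requires the clinician's trial status, not the arm. This stands. A reader might infer that recruiters do know the arm and that selection occurred; the text shows only that no safeguard is described.

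A reader might also infer that investigators recruit families to their own arm. No section says that investigators are randomised; they are described as identifying and approaching eligible clinicians. Their introductions are restricted in frequency, and that limits the channel whatever its motive. The clinical-team route, where a bedside team member judges the moment and introduces the study, is the larger one.

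Other features also limit selection. The study team screens every study ICU bed daily in the electronic record, takes consent itself, and can use the scripted route without the clinical team. The NEST cut-off of 15 applies in both arms. Clinician consent may coincide with the admission of an eligible family, so a clinician's first family may be identified before allocation. If that holds only for the first, three of four families, or 120 of 160, still come after. These features narrow the opening without closing it: a family that the team judges not ready can still go unapproached, and no count by arm is planned that would show it. The monitoring board's listed items cover recruitment goals and dropout, not screening or consent by arm.

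Finally, a common baseline is a recognised choice and gains precision. That is true, but its justification rests on entry being unrelated to arm.

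**Conclusion.** The point holds as an unguarded risk of selection by arm, made more consequential by a model that assumes equal T1 means. It does not hold as a finding that bias occurred or that arms were known.

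If a baseline difference arose and lasted to T2, about 0.23 to 0.68 of it would pass into b2, or 0.7 to 2.0 units for 3 units, with type I error of 6.7% to 26%. The 3 units and the correlation of 0.3 to 0.7 are assumptions; the documents give no value for either. If the difference were present at T1 only, the bias would have the opposite sign, at 0.32 to 0.77 of it.

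A reader might also infer that adding the intervention main effect cures the problem. It does not: it trades one assumption about the imbalance for another and costs precision. Concealment during recruitment and counts by arm matter more than the model change.

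**What to change.** 1. Do not let a randomised clinician introduce the study to their own families.
2. Hide the clinician's arm from coordinators and other introducers until consent and T1 are complete. Role-specific dashboard views are already planned, and the arm is first needed after T1, when results go to intervention clinicians and low NEST scores are handled differently by arm. Intervention attendings know their own arm and cannot be masked, which is why step 1 is needed.
3. Report by arm the numbers screened, approached, consented and NEST-ineligible, and baseline NEST.
4. Pre-specify a sensitivity model that adds an intervention main effect, plus a Black-by-intervention term for Aim 3. State with it that it removes bias only from a lasting imbalance, gives −1.0d for a T1-only imbalance, and raises the SE of b2 from about 1.5–1.8 to 1.9. Keep it as a sensitivity analysis.

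The cost is a portal permission, some wording, counts by arm and one extra analysis; a few introductions may be delayed. The SAP is written in the past tense. If enrolment is complete, steps 1 and 2 can no longer be applied, but step 3, as far as the records allow, and step 4 still can.

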 - b. If a patient is intubated on the day of eligibility but then subsequently extubated the same day, the patient remains eligible for the study as long as consent and T1 are completed within 8 hours of extubation.
- 3. Death must not be imminent (< 24 hours)

Inclusion Criteria (Family Members, Pre-Consent)

- 1. One family member per patient is eligible.
- 2. The family member must be \geq 18 years old.
- 3. The family member must be self-described as the individual (related or unrelated) who provides the most support and with whom the patient has a significant relationship.

Inclusion Criteria (Clinician, Pre-Consent)

1. Patients' bedside ICU attending physicians on the day of family consent are eligible.

Exclusion Criteria (Patients, Pre-Consent)

- 1. Patients who are admitted to an ICU at the index hospital >14 days will be ineligible for participation.
- 2. Patients who are on comfort care or are planned to undergo withdrawal of treatment within the following 48 hours of enrollment will be excluded.
- Prisoners
- 4. Patients who have no known family or surrogate.
- 5. Patients who are transferred to a non-study ICU or non-study clinician will be excluded if they are enrolled into the RCT only.

Exclusion Criteria (Family Members, Pre-Consent)

- 1. Family members will be excluded if they lack English fluency or have other limiting factors that inhibit their ability to use the app (e.g. literacy, blindness, etc).
- 2. Family members will be excluded if they are not directly involved in decision making, are unreachable or unavailable.
- 3. Family members will be excluded if they are <18 years of age.
- 4. Family members will be excluded if they are unable to consent (e.g., dementia, cognitive impairment).
- 5. Prisoners.
- 6. For the RCT only: family members who self-identify as Hispanic and/or self-identify most with a racial group other than White or Black will be excluded.
 - a. Ethnic and racial exclusions do not apply to the ancillary study.

Exclusion Criteria (Patient/Family Dyad Post-Consent)

- 1. Patient dies before T2 is completed.
- 2. Family members will be excluded from the RCT, but not the ancillary study, who have a very low need burden (NEST < 15) after the completion of T1.
- 3. For the primary RCT, participants are also excluded if the randomized physician leaves ICU service or is replaced by a non-participating ICU physician < 2 calendar days after family completes T1.

For Aim 4 RCT (or Aim 3 Ancillary Study) Only:

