General considerations: The primary analyses will be conducted on an intention-to-treat basis; clinicians and patients will be analyzed in the group to which they were randomized, regardless of clinician intervention adherence, using all available data. The main conclusions drawn from this trial will be based on the pre-specified hypotheses outlined below and will be tested with two-sided p-values at the standard 0.05 level. For all study outcomes, we will interpret differences between groups over time with reference to prior literature regarding clinically meaningful changes. Results from exploratory analyses will be interpreted with appropriate consideration for their exploratory nature. Statistical analyses will be performed using the latest release SAS for Windows (Cary, NC) and R/Rstudio.

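### The primary model gives T1 and T2 NEST one common variance although eligibility cuts T1 at 15 and not T2, so the standard error of b2 is wrong whenever the two variances differ

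*Protocol*

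**What the plan says.** Protocol, Data Analysis & Statistical Considerations, Approach to statistical models, stacks the T1 and T2 scores as outcomes. The fixed effects include T2 and T2 × intervention but no intervention main effect, so the arms share a baseline mean. The random part is a family intercept, a physician intercept and one residual: "Both random effects and the residual error (eijk) are assumed to be independent and normally distributed". The outcome is described thus: "Unmet needs will be assessed at T1 and T2 with the total NEST score, a continuous, normally distributed measure". The Aim 3 model has the same random part. Estimation is by maximum likelihood (Missing Data), and the main hypotheses are to be "tested with two-sided p-values at the standard 0.05 level" (General considerations).

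Protocol, Exclusion Criteria (Patient/Family Dyad Post-Consent), removes from the RCT family members "who have a very low need burden (NEST < 15) after the completion of T1". Under Design & Procedures this holds whichever arm the clinician is in. No threshold applies at T2.

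The SAP repeats the normality statement, adds T3 to the NEST assessments and names PROC MIXED. It states no covariance structure. Neither document plans time-specific variances, robust standard errors or an analysis of T2 adjusted for T1.

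**The concern.** A family intercept plus a single residual is a compound-symmetry structure: the fitted variance is the same at both times, whatever the data show. The trial's own eligibility rule works against that, because it removes the lower tail of T1 and leaves T2 uncut. A T1 score cut at 15 also cannot be normally distributed among enrolled families.

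If T2 varies more than T1, the pooled variance understates the noise in the T2 comparison that carries b2. The test of Hypothesis 2a would then reject too often under the null, and its confidence interval would be too narrow. Aim 3 inherits the same structure.

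**Working it through.** **Figures in the plan.** The 0.05 level is a design choice, so there is nothing to reproduce for it. The stated detectable difference for Hypothesis 2a (4.0 to 5.0 units, 160 families, 4 per physician) does not reproduce: 2.80 × 12 × √[(2/80)(1 + 3·ICC)] gives 5.39 at ICC 0.01 and 6.06 at ICC 0.1. That is a separate matter, and nothing below uses it.

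**Inputs from the documents.** Power and sample size considerations says "the standard deviation of the change in NEST score is estimated as 12 units". The ICC is put between 0.01 and 0.1 in the same place. The SD of change fixes only var(T1) + var(T2) − 2·cov = 144, which is one equation in three unknowns. The share below 15 is not given. The related counts are:
- RCT: "to consent approximately 320 patient/family dyads to ensure that 240 patient/family dyads meet all study criteria and are subsequently enrolled". This is 80/320 = 25%, for all post-consent losses together.
- Research Abstract: up to 30 low-need families among 130 controls, 30/130 = 23%, again a cap.
- Ancillary study: 300 consented for 250 enrolled with no NEST threshold. The contrast 1 − (240/320)/(250/300) = 10% also absorbs exclusions that apply only to the RCT, such as replacement of the physician or transfer to a non-study ICU or clinician. It is therefore not a floor.

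**Formula.** Let v1 and v2 be the T1 and T2 variances, c their covariance, and d1 and d2 the arm differences in mean at T1 and T2. The model estimates a common variance s² = (v1 + v2)/2 and ρ = c/s², and then b2 = d2 − ρ·d1.
- True variance is proportional to v2 + ρ²v1 − 2ρc = v2 + ρ²v1 − ρ²(v1 + v2) = v2(1 − ρ²).
- Model variance is proportional to s²(1 − ρ²).
- Ratio R = v2/s² = 2·v2/(v1 + v2). Actual size = 2Φ(−1.96/√R).

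The cut is the same in both arms, so it does not bias b2.

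**Numbers, under assumptions.** Take normal scores, SD 1 at both times before the cut, correlation r and share p cut. With a = Φ⁻¹(p) and λ = φ(a)/(1 − p), v1 = 1 + aλ − λ² and v2 = 1 − r²(1 − v1).

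| Share cut | v1 | v2 (r = 0.3; 0.5; 0.7) | True SE / model SE | Size |
|---|---|---|---|---|
| 5% | 0.81 | 0.98; 0.95; 0.91 | 1.05; 1.04; 1.03 | 6.1%; 5.9%; 5.7% |
| 10% | 0.71 | 0.97; 0.93; 0.86 | 1.07; 1.06; 1.05 | 6.8%; 6.5%; 6.1% |
| 25% | 0.53 | 0.96; 0.88; 0.77 | 1.13; 1.12; 1.09 | 8.4%; 7.9%; 7.1% |

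**Simulation.** The planned model was fitted by maximum likelihood without the stratification covariates: 40 or 60 physicians with 4 families each, ICC 0.01 or 0.1, r = 0.5 or 0.7, 20,000 null trials per setting. Size was 5.0–5.4% with no cut, 5.7–6.4% with 5% cut, 6.1–7.5% with 10% and 7.1–8.9% with 25%. The excess therefore comes mainly from the cut.

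**Departures from the assumptions** (cuts of 5–25%):
- r = 0.8 (formula): 5.5–6.6%.
- Right-skewed scores (gamma, shape 4; simulated): 5.2–7.1%.
- T1, T2 and T3 stacked, as the SAP suggests (formula): 5.5–7.0%.
- T2 SD 15% lower before selection (simulated): 4.2–6.4%.

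At r = 0.5 the variances become equal if the T2 SD before selection is lower by a factor √(0.712/0.928) = 0.88 (10% cut) or √(0.535/0.884) = 0.78 (25% cut). Below that the planned test is conservative.

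**With the variance freed.** Adjusting T2 for T1 and testing at physician level gave 4.8–5.1% in four settings where the planned model gave 5.7–8.9%. The empirical SD of the estimate barely moved (for example 0.1408 against 0.1404). In a separate simulation of 4,000 trials at r = 0.5, an unstructured covariance gave 5.2% (10% cut) and 5.6% (25% cut), against 6.4% and 7.9% for the planned structure.

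**The case against.** The strongest reply is that neither the size nor the direction of the error is established. A reader might infer that the primary test runs at 6–8%. The documents do not support that as a fact, because it needs equal SDs before selection, near-normal scores, a moderate correlation and a sizeable share cut, none of which they give. If needs fall toward a floor by T2, the T2 spread may shrink enough to cancel or reverse the effect.

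A reader might also infer from the counts that 10–25% of families fall below 15. That fails too. The 25% and 23% are ceilings, the 25% includes losses such as death before T2 and departure of the physician, and the 10% contrast is contaminated by other RCT-only exclusions. Shares below 10% fit the documents equally well.

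It is also fair to say that the excess is modest, that b2 is unbiased, and that the two-time formula does not carry over unchanged if T3 is fitted.

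All of this limits the magnitude. It does not rescue the structure: the model still imposes an equality that the eligibility rule gives reason to doubt, and nothing in the Missing Data section or the SAP corrects the standard error.

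**Conclusion.** The point holds as a conditional one. From the documents alone, T1 is truncated by design, T2 is not, the Aim 2 and Aim 3 models force one variance on both, and normality cannot hold for enrolled families' T1 scores. The standard error of b2 is wrong by the factor √[(v1 + v2)/(2·v2)] whenever the variances differ, and truncation of T1 alone makes it too small.

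The tabulated excess, from under 1 point at a 5% cut to about 3 points at the 25% ceiling, rests on the normal, equal-SD and correlation assumptions. Over the wider scenarios tried, size ran from about 4% to 9%. No Aim 3 simulation was run; the point there rests on the shared random part. Bias in the treatment effect should not be inferred. The change is worth making because it is cheap and corrects the standard error whichever variance is larger.

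**What to change.** In the Aim 2 and Aim 3 NEST models, replace the family random intercept and common residual with an unstructured within-family covariance over the time points fitted (in PROC MIXED, REPEATED with TYPE=UN and SUBJECT=family), and keep the physician-level random effect. Analysing T2 adjusted for T1, with the physician effect, is an equivalent route. State the chosen structure and the time points in the SAP, and delete the statement that enrolled families' T1 NEST is normally distributed.

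The SAP is written in the past tense. If the analysis is already done, report this refit beside the planned one.

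The cost is one extra variance parameter with T1 and T2, more if T3 is included, a line of SAP text and code, and almost no loss of precision.
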